1 OBJECTIVES

1.1 Primary Objective

To assess the efficacy of selinexor on spleen volume reduction in subjects with myelofibrosis (PMF, PET-MF, or PPV-MF) refractory or intolerant to ruxolitinib and/or any other experimental JAK1/2 inhibitors.

Primary Endpoint:

Response rate defined as the proportion of subjects with $\geq 35\%$ reduction in spleen volume as measured by MRI or CT abdomen from baseline to after six cycles of treatment. Patients who do not complete six cycles of therapy will be considered non-responders, but their data will still be reported. Patients who do not complete six cycles of treatment will receive an MRI at cycle 7 day 1, or at discontinuation of therapy (see section 11.4.2).

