To date, 12 patients with myelofibrosis were dosed with selinexor in this study. The starting dose of selinexor was 80 mg weekly in the first six patients. After 3 out 6 patients required dose reduction due to grade 2 weight loss. The starting dose of selinexor was decreased to 60 mg weekly for subsequent patients. Additional six patients were enrolled at starting dose of 60 mg weekly. Of all the 12 patients, 7 required dose reduction to 40 mg weekly. Grade 2 weight loss occurred in 5 of 7 patients that required dose reduction to 40 mg weekly. At this time, 4 patients remain on selinexor treatment, 2 on 60 mg weekly dose and 2 on 40 weekly dose. The starting dose of selinexor will be decreased to 40 mg weekly for the remaining 12 expected patients.

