6.4.1 Criteria for Discontinuation of Study Intervention

In addition to the drug-specific discontinuation criteria listed in section 7.2, the following will result in treatment discontinuation:

- Subject withdraws consent from the study treatment and/or study procedures. A subject must be removed from the trial at his/her own request. At any time during the trial and without giving reasons, a subject may decline to participate further. The subject will not suffer any disadvantage as a result.
- Any AE that requires a dose interruption > 28 days.
- Unacceptable AE or toxicity that cannot be managed by supportive care.
- Other AEs or intercurrent illnesses which, in the opinion of the investigator, would be injurious to the health or well-being of the subject and warrant their withdrawal from study treatment.
- Necessity for prohibited treatment (as defined in section 6.3) of sufficient dose and duration to confound the study results.
- Sexually active subjects who refuse to use medically accepted barrier methods of contraception (as defined in section 7.4) during the course of the study and for 3 months after discontinuation of study treatment.
- Women who become pregnant or are breastfeeding.
- Significant non-compliance with the protocol schedule or treatment in the opinion of the investigator.
- Subject is lost to follow-up or dead.
- Request by regulatory agencies for termination of treatment of an individual subject or all subjects under the protocol.

Any patient who does not withdraw from the study but who stops attending study visits and does not respond to 3 documented contact attempts will be considered lost to follow-up.

All patients will be followed until disease progression, withdrawal of consent, occurrence of any withdrawal criteria, loss of clinical benefit or intolerable toxicity precluding further treatment with study treatment, death or loss to follow up.

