Interruption of selinexor therapy, when appropriate, may lead to return of platelet counts in 1 to 3 weeks. See Table 4 for specific guidance for managing Grades 1 through 4 thrombocytopenia. Thrombopoietin agonists, particularly romiplostim at moderate to high doses, have improved platelet counts in heavily pretreated patients receiving selinexor, permitting continued dosing and maintaining anti-neoplastic effects.

Neutropenia

Standard granulocyte growth factors are highly effective for the treatment of neutropenia observed during treatment with selinexor and should be used early in patients whose neutrophil counts decline during treatment. Patients should be instructed to report any symptoms or signs of infection such as fever, pain, sweating, and redness to their physician immediately. If infection during neutropenia is suspected, then standard treatment for febrile neutropenia may be instituted. Selinexor should be interrupted until the patient is clinically stable on appropriate antimicrobial agents. No known interactions with selinexor and antimicrobial agents have been reported, and selinexor may be restarted when the patient's condition has clinically stabilized.

Anemia

Selinexor-induced anemia may contribute to dizziness, confusion, syncope and/or fatigue, particularly in elderly patients and patients who are at greater risk of cognitive sequelae. As per NCCN Guidelines, treatment with red blood cell (RBC) transfusions and/or growth factors, per institutional guidelines, should be considered for patients with symptomatic anemia.

Nausea

In order to minimize nausea, all patients should receive 5-hydroxytryptamine (5-HT3) antagonists (8 mg or equivalent) unless contraindicated, starting on C1D1 before the first dose of study treatment and continued 2 to 3 times daily, as needed. Additionally, olanzapine (2.5 mg or higher) may be given prior to the first dose of selinexor and continued once daily (QD), up to 4 days, as per NCCN Guidelines. Patients with breakthrough nausea or vomiting should receive additional anti-emetic agents.

Infection

No prophylactic antimicrobial agent is recommended for most patients initiating therapy with selinexor. Patients with a history of recurrent infections or those at high risk for specific infections may continue their prophylactic antimicrobial regimens without modification when initiating selinexor therapy.

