Selinexor should be withheld in patients with suspected or active uncontrolled infections, grade 4 infections, or clinical sepsis (in the absence of documented infection). Selinexor treatment can be resumed after initiation of appropriate antimicrobial therapy and when the infection has clinically resolved and/or the patient is clinically stable. When ready to resume selinexor, treatment may continue at the original dose, even in the setting of continued antimicrobial agents.

Diarrhea

Diarrhea associated with selinexor is typically watery and low-grade and usually responds to treatment with standard anti-diarrheal agents (e.g., loperamide) and/or dose modification. Careful assessment of the patient's volume status is essential. Fluid replacement is important to prevent dehydration, fatigue and electrolyte abnormalities (e.g., hyponatremia).

Fatigue

Prevention of anorexia, vomiting, and dehydration may reduce fatigue. Also, as per NCCN Guidelines, the use of methylphenidate 5 mg QD each morning may be helpful. Hemoglobin levels must be optimized as anemia appears to contribute substantially to fatigue, particularly in patients with heavily pretreated hematologic malignancies. In patients with adequate antitumor control on selinexor, QW dosing is often associated with improvement in fatigue and other side effects.

Decreased Appetite

In patients with problematic food/liquid/caloric intake secondary to anorexia, a patient log of food and drink, as well as body weights, should be considered and monitored by site staff. Nutritional counseling is important. Dysgeusia may contribute to the anorexia, and dietary

adjustments can be helpful. Fresh juices and simple carbohydrates, as well as ginger-containing foods and beverages, can improve appetite; ginger-containing foods may also improve dysgeusia. Administration of high caloric beverages (e.g., Boost®, Ensure®) and appetite stimulating agent(s) should be instituted aggressively in patients who develop significant anorexia.

A combination of appetite stimulating agents, particularly olanzapine (2.5 to 5.0 mg every morning), and standard anti-emetics is usually effective in managing selinexor associated anorexia that does not respond to the above interventions. Megesterol acetate 400 mg daily may also be effective. Additional information on the management of anorexia is provided in the NCCN Guidelines.

Hyponatremia

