Grade ≥ 3 with bleeding	
Interrupt selinexor dosing and check platelet counts weekly until the bleeding has stopped, patient is clinically stable and the platelets have recovered to Grade ≤ 3 or baseline. Platelet transfusion is allowed if clinically indicated at the discretion of the principal investigator. When resuming selinexor, reduce by 1 dose level.
 
If recurrent, unless contraindicated, start treatment with moderate to high doses of thrombopoietin stimulating agents as above.

Neutropenia	
Grade 4 neutropenia (afebrile) OR Febrile neutropenia	
Institute colony stimulating factors and prophylactic antibiotics as clinically indicated per institutional guidelines.
 
Interrupt selinexor and check neutrophils at least weekly until recovers to Grade 3 or baseline and without fever (if febrile) and the patient is clinically stable. Colony stimulating factors per institutional guidelines or at the discretion of the principal investigator. When resuming selinexor, reduce by 1 dose level.
 
If recurrent, continue colony stimulating factors, interrupt selinexor until neutrophil counts improve to Grade ≤ 3 or baseline levels. Investigator in consultation with the Medical Monitor may decide to continue selinexor dosing without dose reductions as specified above, provided that CBC and infection symptoms/signs are closely monitored.

Anemia	
Treat per institutional guidelines including blood transfusions and/or erythropoietins. Consider transfusing for symptoms with hemoglobin > 8 g/dL (Grade < 3) or for any Grade 3 (hemoglobin < 8 g/dL). If possible, maintain selinexor dose as long as patient is clinically stable, but if a dose reduction or interruption is desired, it should be done at the discretion of the treating physician and requires authorization from the principal investigator and consultation with the medical monitor if indicated.	
Other clinically significant selinexor-related adverse events	
Grade 1 or 2	Rule out other causes. Maintain dose. Start treatment and/or standard supportive care per institutional guidelines.
Grade 3	
Rule out other causes. Interrupt selinexor until recovers to Grade 2 or baseline and reduce selinexor by 1 dose level.
 
Isolated values of Grade 3 alkaline phosphatase do NOT require dose interruption. Determination of liver versus bone etiology should be made, and evaluation of gamma-glutamyl transferase, 5'-nucleotidase, or other liver enzymes should be performed.

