Grade 4	Permanently discontinue selinexor

^aFor all Grade ≥ 3 hematologic or Grade 3 non-hematologic AEs that are NOT selinexor related, after consultation with the principal Investigator, selinexor, dosing may be maintained.

^bFor all selinexor-related AEs, if the below prescribed dose reductions/interruptions result in a stabilization of ≥ 4 weeks, a re-escalation may be considered at the discretion of the treating physician, and consultation with the medical monitor if indicated, and requires authorization from the principal investigator.

All dose modifications should be based on the worst preceding toxicity.

^cFor all Grade 4 non-hematologic AEs that are NOT selinexor related, selinexor should be permanently discontinued.

Note: When toxicities due to selinexor have returned to baseline levels or the patient has stabilized, the dose of selinexor may be re-escalated at the discretion of the treating physician, and consultation with the medical monitor if indicated, and requires authorization from the principal investigator.

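### After an unrelated Grade 4 infection, the section 7.2 Infection text allows full-dose resumption while Table 4 footnote c calls for a permanent stop; restart guidance after febrile neutropenia also differs

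*Combined protocol and SAP*

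**What the plan says.** All of this guidance sits in protocol section 7.2, partly in narrative paragraphs and partly in Table 4 and its footnotes. Section 7.1 sends sites to both.

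**Grade 4 infection**
- The Infection paragraph withholds drug for suspected or uncontrolled infection, for Grade 4 infection and for clinical sepsis. It allows resumption once antimicrobials have been started and the infection has resolved or the patient is stable. On dose it says: "When ready to resume selinexor, treatment may continue at the original dose, even in the setting of continued antimicrobial agents". It makes no distinction by relatedness.
- Table 4 footnote c calls for permanent discontinuation for all Grade 4 non-hematologic events not related to selinexor.

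**Febrile neutropenia with suspected infection**
- The Neutropenia paragraph says: "Selinexor should be interrupted until the patient is clinically stable on appropriate antimicrobial agents". It adds that "selinexor may be restarted when the patient's condition has clinically stabilized". It names no neutrophil level, no fever condition and no dose.
- The Table 4 row for Grade 4 or febrile neutropenia asks sites to interrupt and "check neutrophils at least weekly until recovers to Grade 3 or baseline and without fever (if febrile) and the patient is clinically stable". Dosing then resumes one level lower.
- A sentence among the table footnotes adds: "All dose modifications should be based on the worst preceding toxicity".

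**The concern.** These are decisions about re-dosing during or just after a serious infection, in patients who may enter with a neutrophil count as low as 500/mm³ (section 5.1.6). Two investigators can each follow section 7.2 and do different things. After an unrelated Grade 4 infection, one resumes at full dose and the other stops for good. After a first related febrile neutropenia, one restarts at full dose before neutrophils recover, and the other waits and reduces. A monitor would have no clear basis for saying which of them complied.

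**Working it through.** The plan states no figure on this point, so the check is a comparison of texts. The only arithmetic concerns dose.

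**Main case: Grade 4 infection, not related to selinexor**
1. The Infection paragraph applies, because it names Grade 4 infection. It permits the original dose.
2. Footnote c applies, because infection is a non-hematologic event, the grade is 4 and the event is unrelated. It calls for a permanent stop.
3. Clauses that might reconcile the two:
   - Section 7.1 refers to section 7.2 and Table 4 together and ranks neither.
   - Footnote a lets dosing continue after unrelated non-hematologic events, but only at Grade 3.
   - Section 7.2.1 gives discretion only for events not listed in section 7.2, and infection is listed there.
   - Footnote b and the closing note deal with re-escalation after a reduction or interruption. They do not lift a permanent stop.
   - The worst-toxicity sentence does not choose between the two.
4. Size per patient: at 40 mg weekly, 4 doses × 40 mg = 160 mg per 28-day cycle under the paragraph, against 0 mg under the footnote.

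**Lesser case: first selinexor-related febrile neutropenia with suspected infection**
1. Restart condition: the text asks for clinical stability on antimicrobials. The table asks for clinical stability, neutrophils at Grade 3 or baseline, and no fever.
2. Restart dose: the Neutropenia paragraph is silent and the Infection paragraph permits the original dose. The table reduces by one level.
3. Clauses that might reconcile the two:
   - The worst-toxicity sentence favours the table on dose but does not reach the restart condition.
   - The option in the row to dose without reduction applies on recurrence.
   - The Thrombocytopenia paragraph refers to Table 4 for its management. The Neutropenia and Infection paragraphs do not.
   - The sentence introducing Table 4 presents it as covering other related events, which might suggest that the narrative governs events it has already discussed. But the table has its own neutropenia row.
4. Size per patient, from Table 3:
   - 20 against 40 mg weekly: 20/40 = 0.50, a 50% lower dose.
   - 40 against 60 mg weekly, after an escalation: 40/60 = 0.67, a 33% lower dose.
   - The hold cannot exceed 28/7 = 4 weekly doses before treatment ends under section 6.4.1. This is a ceiling, since both sources already wait for clinical stability.

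**The case against.** Section 7.2 is guidance, and the narrative is permissive. A site that follows the Table 4 neutropenia row breaches neither paragraph, and silence on dose in the Neutropenia paragraph is not an opposing instruction. This largely stands. It makes the febrile neutropenia case a mismatch rather than a flat contradiction, and with the worst-toxicity sentence it gives the dose a workable answer. It leaves open when to restart.

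For Grade 4 infection, one can argue that the specific paragraph is an exception to a general footnote. That is a sensible reading, but the footnote covers all such events and the plan does not state the exception. A site could as reasonably take the stricter rule.

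The events may also be uncommon at these doses. Section 2.3.3 reports Grade 3-4 neutropenia in the Phase 1 trial mainly at 60 mg/m² per week or more (about 100 mg by that section's own conversion), and no overall rise in infections. The exception was sepsis in elderly AML patients given more than 60 mg. Patients enrolled under version 7 start at 40 mg and escalate at most to 60 mg weekly. Those populations are not myelofibrosis, so this does not establish rarity, but it argues against presenting the problem as frequent.

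The medical monitor is notified of serious adverse events and the DSMC reviews them monthly (section 15.4). This limits harm but does not give the treating investigator one rule.

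**Conclusion.** The conflict on unrelated Grade 4 infection is real and unresolved in the current text: full dose or permanent stop. The febrile neutropenia mismatch is real but softer, and lies mainly in the restart condition. The conclusion assumes that infection counts as non-hematologic and that the investigator's relatedness judgement decides which clause applies. The dose figures assume the Table 3 levels for patients enrolled after version 7.

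A reader might infer three stronger things that the documents do not support.
- *Every Grade 4 infection meets contradictory instructions.* For a related infection this holds only if the Grade 4 row for other related events is read to include infection. Table 4 has no infection row.
- *All patients still to be treated are affected.* Section 2.3.3 says: "The starting dose of selinexor will be decreased to 40 mg weekly for the remaining 12 expected patients". That describes who could be exposed to the ambiguity, not how many will have these events.
- *The primary result is distorted.* A path exists. Treatment ends for "Any AE that requires a dose interruption > 28 days", and section 1.1 says: "Patients who do not complete six cycles of therapy will be considered non-responders, but their data will still be reported". But the event must occur before six cycles are complete, the choice of wording must cause the stop, and the patient must otherwise have responded. The documents give no probability for any of these steps. The primary test and the sample size are unchanged.

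This is a low-cost safety clarification of unknown frequency, worth making.

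**What to change.** **Grade 4 infection.** Make the Infection paragraph and footnote c agree. The investigators and medical monitor should choose between:
- permanent discontinuation, by taking Grade 4 infection out of the resumption wording in the Infection paragraph; or
- resumption, by writing into footnote c an explicit exception for Grade 4 infection that has resolved or is clinically stable and, for consistency, repeating it in the Grade 4 row for other related events.

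Either removes the conflict. The choice is clinical.

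**Febrile neutropenia.** Add one sentence to both the Neutropenia and Infection paragraphs: for selinexor-related Grade 4 or febrile neutropenia, the Table 4 neutropenia row governs the restart condition and the dose, including its provision for recurrence. Leave the clinical-stability condition in the Neutropenia paragraph in force for unrelated cases. Do not route those cases to footnote a, which has no restart condition.

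**Cost.** The change is to wording and adds no tests, since Table 4 already asks for neutrophil counts at least weekly. Because it affects dosing, it needs DSMC review and PRMC and IRB approval (section 15.4). Some patients will restart later, or at 20 instead of 40 mg weekly (40 instead of 60 mg after escalation), and a few may pass the 28-day limit. Re-escalation remains available under footnote b. If permanent discontinuation is chosen, patients stopped before six cycles count as non-responders.

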7.2.1 Conditions Not Requiring Selinexor Dose Reduction

The following conditions are exceptions to the dose-modification guidelines and do not require a dose reduction or delay:

- Alopecia of any grade
- Electrolyte or serum analyte (e.g., urate) abnormalities that are reversible with standard interventions
- Isolated values of Grade ≥ 3 alkaline phosphatase. Determination of liver versus bone etiology should be made, and evaluation of gamma-glutamyl transferase, 5'-nucleotidase, or other liver enzymes should be performed.

In addition, selinexor dosing may be maintained in case of grade ≥ 3 hematological or non-hematological AEs not listed above (in Section 7.2) at the discretion of the enrolling physician and after consultation with the Sponsor-Investigator and the DSMC medical monitor.

